10.3. Communication Between Investigational Sites

Investigational sites will be required to report problems with study drug administration or any other problem that could affect the validity/integrity of the study data to the Sponsor-Investigator by email as soon as possible but within 2 business days of the Investigator learning of the event. All investigational sites will record AEs using the eCRFs and SAEs using the SAE reporting function in the CTMS to the Sponsor. SAEs will be reported to the Sponsor-Investigator within 24 hours of the Investigator learning of the event.

10.4. Clinical Trial Registration

This study will be registered on the National Library of Medicine/National Institutes of Health ClinicalTrials.gov website. This trial will be initially registered prior to enrollment of the first subject. Trial's progress and results will be updated as necessary, but at least once every 6 months. Summary results of the trial will be submitted to the ClinicalTrials.gov website within 12 months of final data collected of the primary endpoint.

11. SAFETY DATA COLLECTION, RECORDING AND REPORTING

11.1. Unanticipated Problem (UAP) Definition

An unanticipated problem (UAP) is any incidence, experience or outcome that is unexpected, given the information provided in research-related documentation (e.g Investigator's brochure, informed consent) and the study population characteristics

that is related or possibly related to participation in the research study and places the participant at an increased risk.

11.2. Adverse Event (AE) Definition

An adverse event (AE) is defined as any untoward medical occurrence, including an exacerbation of a pre-existing condition, in a subject in a clinical investigation who received a pharmaceutical product. The event does not necessarily have to have a causal relationship with this treatment. An adverse event can therefore be any unfavorable and unintended sign, symptom, or disease temporally associated with the use of the study drug, whether or not considered related to the study drug. Pre-existing conditions that increase in frequency or severity or change in nature during or as a consequence of use of a drug in human clinical trials are also considered adverse events. Adverse events may also include pre- or post-treatment complications that occur as a result of protocol mandated procedures.

Any continuing medical condition or clinically significant laboratory abnormality with an onset date before the date of informed consent should be documented in the subject's medical records and/or research chart.

Examples of events not meeting the definition of an adverse event include:

- medical or surgical procedures
- pregnancy (unless this is associated with an SAE)
- relapse or progression of the underlying malignant disease

The relationship to study drug should be assessed using the following definitions:

Not Related: Evidence exists that the AE has an etiology other than the study drug (eg, pre-existing condition, underlying disease, intercurrent illness, or concomitant medication). This includes events that are considered remotely or unlikely related to study drug.

Related: A temporal relationship exists between the event onset and administration of the study drug. It cannot be readily explained by the subject's clinical state, intercurrent illness, or concomitant therapies. In the case of cessation or reduction of the dose, the event abates or resolves and reappears upon rechallenge. It should be emphasized that ineffective study drug treatment should not be considered as causally related in the context of AE reporting. This includes events that are considered possibly, probably, or definitely related to study drug.

All adverse events (including event name, grade, start/stop date and attribution) will be documented in the medical record and/or research chart and on the case report form for this protocol.

Adverse Events of Special Interest (AESI) Definition

The following will be considered an AESI:

- an elevation of ALT and / or AST > 5x ULN without bilirubin elevation measured in the same blood draw sample.
- an elevation of AST and/or ALT >2.5x ULN combined with an elevation of bilirubin to >1.5x ULN measured in the same blood draw sample.
- any gastrointestinal- and non-gastrointestinal perforation, leakage, fistula formation, abscess.

In such case the following additional information is recommended to be collected, documented in the respective comment field and narratives of the BI SAE Report Form, and forwarded to BI:

- location of perforation, leakage, fistula, abscess
- location/extent of abdominal tumour manifestations,
- imaging & reports (CT, ultrasound, endoscopy, pathology, etc)
- prior surgery (location, wound healing complications)
- concomitant diseases with GI involvement (eg, M Crohn, vasculitis, tuberculosis,
- diverticulitis)
- thromboembolic events (or predisposition)

Please refer to Appendix A for recommended procedures for drug induced liver injury.

11.3. AESIs are to be reported in an expedited manner similar as Serious Adverse Events, even if they do not meet any of the seriousness criteria and documented in the eCRF. Serious Adverse Event (SAE) Definition

An AE is to be considered serious if the Investigator (in consultation with the Sponsor-Investigator if needed) deems it as such and the event results in any of the following outcomes:

- Death (fatal);
- Life-threatening situation (subject is at immediate risk of death);
- Persistent or significant disability/incapacity;
- Requires or prolongs inpatient hospitalization (excluding those for study drug administration, protocol-related procedures, palliative or hospice care, or placement of an indwelling catheter, unless associated with other serious events;

- A congenital anomaly/birth defect in the offspring of a subject who received study drug;
- Or based upon appropriate medical judgment, may jeopardize the subject and may require medical or surgical intervention to prevent one of the afore listed outcomes from occurring (e.g. intensive treatment in an emergency room without hospitalization, blood dyscrasias or convulsions that do not result in hospitalization, development of drug dependency or drug abuse).

The following events do not meet the criteria for seriousness per ICH definition, but must be reported in the same manner as SAEs. Therefore, these events are considered serious for collection purposes:

- Drug exposure during pregnancy

Subjects may be hospitalized for administrative or social reasons during the trial. These and other hospitalizations planned at the beginning of the trial do not need to be reported as an SAE.

The severity of adverse events should be classified and recorded according to the Common Terminology Criteria for Adverse Events (CTCAE) version 4.03 in the eCRF.

An increase in grade to a pre-existing CTC toxicity after study treatment initiation will be recorded as an AE.

Changes in vital signs, ECG, physical examination and laboratory test results will be recorded as an AE if they are judged clinically significant by the investigator.

11.4. Adverse Event and Deviation Reporting

11.4.1. Reporting to the Sponsor (LCI)

All adverse events from the time of study treatment initiation until 30 days after last dose of study drug (including event name, grade, start/stop date and attribution) will be documented in the medical record and/or research chart and recorded on the case report form for this protocol.

The investigator is responsible for verifying and providing source documentation for all adverse events and assigning the attribution for each event for all subjects enrolled on the trial.

Protocol-specified AESI are to be reported in an expedited manner similar to Serious Adverse Events, even if they do not meet any of the seriousness criteria.

SAEs and AESIs must be reported to the Sponsor-Investigator within 24 hours of awareness via the CTMS.

Information not available at the time of the initial report which is received after the initial report must be documented on a follow-up SAE utilizing the same process described above for reporting the initial SAE/AESI. For expedited reporting involving drug exposure during pregnancy, a follow-up report to describe the outcome of the pregnancy is required within 24 hours of investigator awareness.

SAEs will be captured from the time of signing of the informed consent through 30 days after the date of the last study drug administration. SAEs and AESIs will be followed until clinical recovery is complete, laboratory tests have returned to baseline, or until there has been acceptable resolution of the event. This may at times cause the follow-up period for SAEs and AESIs to be greater than 30 days. The above referenced 30-day time period applies even if the subject is taken off treatment and initiates subsequent anti-cancer treatment during this time period. Similarly, the treating investigator is responsible for following the subject during the required follow-up period even if the subject lives elsewhere or has been released from his or her care.

Deviations from the investigational plan must be reported to the sponsor via entry into the CTMS as soon as they occur, but within no more than 10 business days of becoming aware of the event (as soon as possible for deviations reportable to the IRB).

11.4.2. Safety Reporting to the IRB

All events occurring during the conduct of a protocol and meeting the definition of an UAP or related and unexpected SAE will be reported to the IRB per their reporting requirements.

Protocol deviations that are determined by the Investigator to potentially cause harm to participants or others or indicate that the participants or others are at an increased risk of harm, or have adversely impacted data integrity will be reported promptly to the IRB per their reporting requirements.

11.4.3. Safety Reporting to Funding Company (Boehringer Ingelheim Pharmaceuticals Inc.)

During the conduct of the study the Sponsor-Investigator shall report all

- i. SAEs,
- ii. AESIs independent of their seriousness,
- iii. and non-serious AEs which are relevant to a reported SAE or AESI
- iv. Pregnancies

by fax or other secure method using BI IIS SAE form providing as much detail as possible (pregnancies using Pregnancy Monitoring Form) to the BI Unique Entry Point in accordance with the timelines specified below as per the Pharmacovigilance agreement.

- within five (5) calendar days of the Sponsor-Investigator's knowledge of initial and follow-up SAEs containing at least one (1) fatal or immediately life-threatening event;
- within ten (10) calendar days of the Sponsor-Investigator's knowledge of any other initial and follow-up SAEs
- Pregnancy Monitoring Forms shall be forwarded within seven (7) days of Sponsor-Investigator awareness of the pregnancy

BI Unique Entry Point:

Boehringer Ingelheim Pharmaceuticals, Inc
[name]
[name]
[contact]
E-mail: [contact].

With receipt of follow-up information, all remaining fields on the SAE form are to be completed or updated.

The investigator does not need to actively monitor the study subjects for adverse events once the clinical trial has ended. However, if the investigator becomes aware of an SAE(s) or AESI(s) that occurred after the adverse event reporting period as defined in Section 11.4.1 (including any protocol specified follow-up period/Residual effect period), it should be reported to BI if the investigator considers it as relevant to the BI study drug.

11.4.4 Other Reporting

The IRB and Boehringer Ingelheim Pharmaceuticals (BI) will be notified in writing of other events according to the following schedule:

Table 5: Reporting to IRB and BI

Event	Agency	Timeframe for Reporting
Minor changes to the investigational plan	IRB	Within 90 days of SI becoming aware of change
	BI	Prior approval needed
Major changes to the investigational plan (also known as amendments)	IRB	Prior approval needed
	BI	Prior approval needed
Annual Report	IRB	Annually at time of IRB approval
	BI	Annual IRB approval letter to be provided to BI.
Final Report	IRB	Part of study termination submission
	BI	Within 60 days after study completion

12. MEASUREMENT OF EFFECT

12.1. Anti-tumor Effect – Solid Tumor

Response and progression will be evaluated in this study using the revised response evaluation criteria in solid tumors (RECIST) guideline version 1.1¹.

12.1.1. Methods for Evaluation of Measurable Disease

All measurements should be taken and recorded in metric notation using a ruler or calipers. All screening evaluations should be performed as closely as possible to the beginning of treatment and never more than 4 weeks before the beginning of the treatment.

The same method of assessment and the same technique should be used to characterize each identified and reported lesion at screening, during treatment and follow-up. Imaging-based evaluation is preferred to evaluation by clinical examination when both methods have been used to assess the anti-tumor effect of a treatment.

12.1.2. Response Criteria

Response will be evaluated using RECIST 1.1 Criteria.

Complete Response:

- Target lesion: Disappearance of all target lesions. Any pathological lymph nodes (whether target or non-target) must have reduction in short axis to <10 mm.
- Non-target lesion: Disappearance of all non-target lesions. All lymph nodes must be non-pathological in size (<10 mm short axis).

Partial Response:

- Target lesion: At least a 30% decrease in the sum of diameters of target, taking as reference the baseline sum diameters.
- Non-target lesion: Not applicable

Stable Disease:

- Target lesion: Neither sufficient shrinkage to qualify for a partial response, nor sufficient increase to qualify for progressive disease, taking as reference the smallest sum diameters while on study.
- Non-target lesion: Not applicable.

Progressive Disease:

- Target lesion: At least a 20% increase in the sum of diameters of target lesions, taking as reference the *smallest sum on study* (this includes the baseline sum if that is the smallest on study). In addition to the relative increase of 20%, the sum must also demonstrate an absolute increase of at least 5 mm. (*Note:* the appearance of one or more new lesions is also considered progression).
- Non-target lesion: *Unequivocal progression* (as described in RECIST version 1.1) of existing non-target lesions. (*Note:* the appearance of one or more new lesions is also considered progression).

Non-Complete Response / Non-Progressive Disease:

- Target lesion: Not applicable
- Non-target lesion: Persistence of one or more non-target lesion(s)

Table 6: Summary of RECIST

Target Lesions	Non-target Lesions	New Lesions	Overall Response	Best Response for this Category also requires
CR	CR	No	CR	Documented at least once ≥ 4 weeks from baseline
CR	Non-CR/Non-PD	No	PR	Documented at least once ≥ 4 weeks from baseline
CR	Not evaluated	No	PR	
PR	Non-PD or not all evaluated	No	PR	
SD	Non-PD or not all evaluated	No	SD	Documented at least once ≥ 4 weeks from baseline
Not all evaluated	Non-PD	No	NE	N/A
PD	Any	Yes or No	PD	No prior SD, PR or CR
Any	PD*	Yes or No	PD	
Any	Any	Yes	PD	
* In exceptional circumstances, unequivocal progression in non-target lesions may be accepted as disease progression CR = Complete Response, PR = Partial Response, SD = Stable Disease, PD = Progressive Disease, and NE = inevaluable				

Table 7: Overall Response for Subjects with Non-measurable disease only

Non-target Lesions	New Lesions	Overall Response
CR	No	CR
Non-CR/ Non-PD	No	Non-CR/ Non-PD
Not all evaluated	No	NE
Unequivocal PD	Yes or No	PD
Any	Yes	PD

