1.2. Secondary Objectives

The secondary study objectives are to evaluate:

- Safety and toxicity,
- Objective response rate,
- Overall and 6-month progression free survival, and
- Overall survival

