The predominant adverse events were nausea, diarrhea, vomiting, abdominal pain and fatigue of mostly low to moderate severity. Dose limiting toxicities (DLT) were mainly confined to reversible hepatic enzyme elevations (AST, ALT, γ -GT) which increased dose-dependently. Most cases occurring at doses of 250 mg and above, and a very low incidence at doses below 200 mg and were reversible after discontinuation of nintedanib treatment. All adverse events observed after single administration of single doses of nintedanib to healthy volunteers were only of CTCAE grade 1 severity and fully reversible¹¹.

NSCLC

In a phase II trial in NSCLC patients the safety profile of nintedanib observed in phase I trials could be confirmed. Most commonly reported drug-related AEs were

nausea (57.5%), diarrhea (47.9%), vomiting (42.5%), anorexia (28.8%), abdominal pain (13.7%) and reversible alanine transaminase (13.7%) and aspartate aminotransferase elevations (9.6%) In conclusion it was generally well tolerated and displayed single agent activity in advanced or recurrent NSCLC patients. Median overall survival (OS) was 21.9 weeks. Eastern Cooperative Oncology Group (ECOG) 0–1 patients (n = 56) had a median PFS of 11.6 weeks and a median OS of 37.7 weeks. Tumour stabilisation was achieved in 46% of patients (ECOG 0–1 patients: 59%), with one confirmed partial response (250 mg bid.)¹³.

LUME-Lung 1 was an international, randomized, double-blind, phase III trial assessing the efficacy and safety of docetaxel plus nintedanib as second line therapy for non-small-cell lung cancer (NSCLC). In total, 1314 patients with Stage IIIB/IV or recurrent NSCLC (all histologies) who had progressed after 1st line chemotherapy were randomized in 1:1 fashion to either receive Nintedanib 200mg BID + Docetaxel (n=655) or Placebo BID + Docetaxel (n=659).

LUME-Lung 1 met its primary endpoint by showing a statistically significant improvement of PFS for all patients regardless of histology (median PFS 3.4 versus 2.7 months; HR 0.79, p=0.0019) for nintedanib in combination with docetaxel¹⁰.

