5.2. Overall Study Design

This is a single arm, two-stage phase II study designed to evaluate disease control rate in subjects with metastatic appendiceal carcinomas who have had failure of initial fluoropyrimidine-based chemotherapy.

In the first stage, a total of 28 subjects in the evaluable population will be enrolled. Of these, if at least 8 should achieve disease control (Section 13.1.1) the study will continue on to the second stage. In the second stage, 11 participants in the evaluable population (total of 39) will be enrolled. If at least 16 of the 39 total subjects enrolled achieve disease control, then we will be able to reject the null hypothesis. The sample size of evaluable population for both Stage 1 and Stage 2 include participants who begin nintedanib therapy.

Following informed consent and eligibility check, subjects will be enrolled and treated with 200mg of oral nintedanib two times per day and undergo disease evaluation after two months. Subjects who progress will be discontinued from study treatment and those who do not progress will continue twice daily treatment with nintedanib and will continue to undergo disease evaluation every two cycles.

Data from this study will be collected on electronic case report forms (eCRFs) and stored in the clinical trials management system (CTMS).

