Specimens will be collected according to the schedule in Section 6. Specimens will be collected after subject eligibility confirmation, but prior to administration of the first dose of nintedanib and subsequent cycles. Exploratory biomarker arrays may be used.

Radiology and Tumor Measurements. A computed tomography (CT) scan with oral and intravenous contrast of the chest, abdomen and pelvis will be performed within 28 days prior to the first dose of nintedanib (screening scan). Scans will then be performed within 7 days following anticipated completion of cycle 2 unless clinically proven otherwise and within 7 days of anticipated completion of every two cycles thereafter (e.g. end of cycles 4, 6). A contrast-enhanced MRI of the abdomen and pelvis and a CT scan of the chest without contrast may be substituted if clinically necessary; however, subsequent studies must be performed using the same imaging modality throughout the study period.

For subjects who discontinue study therapy due to toxicity or reasons other than progressive disease, every effort will be made to obtain imaging studies and tumor assessments every 8 weeks (+/- 2 weeks) until documented progression or the start of subsequent anti-cancer therapy.

Subsequent Therapy and Survival Status. Once subjects complete their End of Treatment visit, they will be followed until all treatment-related toxicities have resolved, returned to baseline, stabilized, or are deemed irreversible. Subject's initial anti-cancer therapy following discontinuation of nintedanib treatment and survival

status will be documented.

Subjects (or their family members or designees) may be contacted by telephone, in writing, or during clinic visits after treatment discontinuation for collection of long-term follow-up data approximately every 6 months until death or lost to follow-up, or until the criteria defined for the final analysis (Section 13.3.1) are reached. However, in the event the criteria for the final analysis are met, and there are subjects who have not yet been discontinued from nintedanib treatment, subjects in follow up will continue to be followed until all subjects have discontinued study treatment and completed the safety monitoring period. Long-term follow-up clinical information may also be obtained through chart reviews.

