13.1.2. Objective Response

Objective response will be determined for each subject as a binary variable indicating whether or not the subject achieved a best overall response of CR or PR as determined by RECIST 1.1.

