13.2. Analysis Populations

The response-evaluable population for the analysis of objective response will include enrolled subjects with measurable disease at baseline. The evaluable population for the analysis of disease control, all other secondary endpoints, and safety endpoints will include subjects who begin nintedanib treatment. The sample size requirements for

Stage 1 and 2 described above pertain to the evaluable population for the analysis of disease control.

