13.3.4.2. Secondary Analyses

Objective response rate and 6-month PFS rate will be estimated with the corresponding 95% Clopper-Pearson confidence interval.

Progression-free survival and overall survival rates will be estimated using Kaplan-Meier techniques.

Multivariable regression models (logistic regression for binary variables and Cox proportional hazards models for time to event variables) will be used to evaluate the impact of correlative biomarkers, and baseline subject and disease characteristics on outcomes. Additionally, nintedanib exposure will be considered as a covariate.

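### A complete or partial response seen on a single scan counts as an objective response, so measurement error over repeated scans can bias the secondary response rate upward; a confirmed rate should be reported beside it.

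*Combined protocol and SAP*

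**What the plan says.** Objective response rate is a secondary objective (section 1.2). Section 13.1.2 makes it a yes/no variable for whether the subject "achieved a best overall response of CR or PR as determined by RECIST 1.1". For CR and PR, Table 6 in section 12.1.2 requires that the category be "Documented at least once ≥ 4 weeks from baseline", the same requirement as for SD. The rate is estimated with a 95% Clopper-Pearson interval (section 13.3.4.2) in a population that "will include enrolled subjects with measurable disease at baseline" (section 13.2). It has no hypothesis, target or decision rule.

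The design has one arm: "This is a single arm, two-stage phase II study" (section 5.2). Under section 5.5, scans fall at the end of cycle 2 and then "within 7 days of anticipated completion of every two cycles thereafter". With 28-day cycles that is about every 8 weeks. Subjects who stop treatment for reasons other than progression are to be scanned about every 8 weeks on a best-effort basis, until progression or new therapy.

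**The concern.** Best response is the best category reached over all scans. Each scan gives a subject whose tumour has not truly shrunk by 30% another chance to cross that line through measurement error, and a later reading that reverses it does not undo the response. With no concurrent arm, the trial cannot show how many responses arise in this way.

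The response-evaluable group has at most 39 subjects. If true responses are few, one false one changes the message from no responses seen to some activity seen.

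**Working it through.** **The plan's own figure.** The only operating characteristics stated are for disease control (section 13.1): continue with at least 8 of 28, reject with at least 16 of 39, one-sided alpha 0.10, power at least 90%. With X ~ Bin(28, p) and Y ~ Bin(11, p), P(reject) = Σ over x ≥ 8 of P(X = x)·P(Y ≥ 16 − x). This gives 0.0943 at p = 0.30 and 0.9001 at p = 0.50, so the design reproduces. Confirmation does not enter it, because disease control counts CR, PR and SD alike.

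**False responses when tumour size has not changed.** The plan gives no figure for measurement error or for the number with measurable disease, so these are assumptions:
- Let S be the SD of log(follow-up sum / baseline sum), with range 0.07 to 0.20.
- Baseline error b and each follow-up error are independent normal with SD s = S/√2, so all changes share the baseline error.
- Three scans, at about weeks 8, 16 and 24; 30 of 39 subjects with measurable disease.
- A PR is read when the log change is at or below ln 0.7 = −0.357.

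Given b, the chance of a PR at one scan is p(b) = Φ((−0.357 + b)/s). Averaging over b:
- PR at any of three scans: E[1 − (1 − p)³]
- PR at two consecutive scans: E[2p² − p³]

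| S | Any of 3 scans | Two consecutive | Expected among 30, unconfirmed | Expected among 30, confirmed |
|---|---|---|---|---|
| 0.07 | about 0 | about 0 | about 0 | about 0 |
| 0.10 | 0.05% | 0.001% | 0.02 | about 0 |
| 0.12 | 0.42% | 0.02% | 0.13 | 0.005 |
| 0.15 | 2.3% | 0.18% | 0.70 | 0.06 |
| 0.20 | 9.1% | 1.3% | 2.7 | 0.4 |

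**Allowing for progression.** Subjects who progress stop treatment, and section 13.1 works with disease control of 30% (null) to 50% (target). If only that share of the 30 is progression-free at the first scan, 9 to 15 subjects remain at risk of a false PR. Even if all of these have three scans, expected false responders are 9 × 2.3% to 15 × 2.3% = 0.21 to 0.35 at S = 0.15, and 9 × 9.1% to 15 × 9.1% = 0.8 to 1.4 at S = 0.20. They are essentially nil at 0.10 and below.

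**What one responder does to the estimate (Clopper-Pearson).** 0/30 is 0% (95% CI 0 to 11.6%); 1/30 is 3.3% (0.1 to 17.2%).

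**With some true shrinkage.** Suppose the true change has mean 0 and SD 15%, constant over time, so that 2.3% of subjects truly shrink by 30% or more. With three scans and removal at progression, the expected rates are:

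| CV per measurement | Unconfirmed | Confirmed |
|---|---|---|
| 5% | 4.4% | 2.4% |
| 10% | 9.6% | 3.5% |
| 15% | 17.6% | 5.4% |

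The confirmed rate still exceeds 2.3% when error is large, because both scans share the baseline reading. If only 60% of subjects are retained at each later scan (also assumed), the confirmed rate at 5% CV falls to 1.4%, below the true 2.3%.

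**The case against.** **The rule is a deliberate choice, stated consistently.** Table 6 and section 13.1.2 agree, and nothing in the trial is decided on the response rate. This stands. The point concerns how the rate is reported; the documents do not contradict themselves.

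**The size is assumed.** This also stands. Sections 5.5 and 12.1.1 require the same modality and technique throughout, which limits error, and the effect almost vanishes at S = 0.10 or below. One or more expected false responders arises only towards the upper end of the range. The documents also give no expected response rate in appendiceal cancer, so that it will be low is an inference.

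**Confirmation has its own bias.** A true responder who progresses, dies, withdraws or starts new therapy before the next scan, about 8 weeks later, is not confirmed. Scans after stopping treatment are best-effort only. This argues against making the confirmed rate the only headline and in favour of showing both.

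**Stronger readings that the documents do not support.**
- A reader might infer that the primary result is inflated too. It is not: a PR that fails confirmation would still be at least SD under section 13.1.1.
- A reader might infer an unlike comparison with the earlier lung cancer trial, whose single partial response section 2.2.2 describes as confirmed. That trial is cited as background and for dose rationale (section 2.3.2), and the plan never compares response rates with it. The only historical benchmark is the 30% disease control rate.
- A reader might infer that confirmation costs nothing because the next scan is already scheduled. That holds for the number of scans, but not for the estimate, as the retention example shows.

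**Conclusion.** The point holds as a minor one. The single-scan rule is current text, no section adds confirmation, and the unconfirmed rate exceeded the true rate in every scenario with true shrinkage that was tried. For S of 0.07 to 0.20 and 30 measurable subjects, expected false responders are about 0 to 2.7 with three scans for all, and about 0 to 1.4 once progression at the first scan is allowed for. These figures rest on assumed measurement error, an assumed number with measurable disease and an assumed scan count. Only the secondary objective response rate is affected.

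**What to change.** In sections 13.1.2 and 13.3.4.2:
- Report two rates, each with a Clopper-Pearson interval: the unconfirmed rate as now defined, and a confirmed rate counting a CR or PR only if it is still present at the next scheduled scan, at least 4 weeks later.
- List separately the responders who have no later scan, so that the reader can see how far loss of follow-up lowers the confirmed rate.
- State that an unconfirmed CR or PR still counts as disease control, so that the primary endpoint does not change.

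The cost is wording in these sections, one extra table line and a short listing. No scans are added. The drawback is that the confirmed rate may miss true responders who stop before the next scan; showing it beside the unconfirmed rate makes that visible.
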